Cancer epidemiology and screening rates. There are continued disparities in cancer incidence, mortality, and survival between AIs and Whites on cancers responsive to early screening (i.e., breast, colon-rectum [CR], and cervical) and prostate cancer in the United States (U.S.). For the period 1990-2009, based on data from Contract Health Service Delivery Area Counties across the U.S., the mortality-to-incidence ratios (indicator of survival) for these cancers were significantly higher for American Indian/Alaska Natives compared to Whites (breast: 1.22, CR: 1.16, cervix: 1.36, prostate: 1.40)⁵, indicating poorer survival. AIs in New Mexico also experience substantial cancer health disparities. For the period 2010-2014, AIs compared to Whites had higher incidence rates (per 100,000) for cervical (7.9 vs. 6.9) and CR (male: 46.5 vs. 35.2; female: 29.2 vs. 28.2) cancers, and higher mortality rates for cervical (3.7 vs. 1.3) and CR (males only; 18.9 vs. 15.6) cancers⁶. AIs were also more likely to receive a late-stage (i.e., regional or distant)

cancer diagnosis for all three screen detectable cancers⁷. AIs have some of the lowest cancer screening rates compared with other racial/ethnic groups. In New Mexico, AIs listed in the IHS Albuquerque Area have substantially lower screening rates than the state's White population do. AIs had screening rates of: breast (58.5%, women ages 52-64), CR (41.9%, ages 50-75), and cervical (63.9%, women ages 24-64) cancers¹; whereas, screening rates for Whites were: breast (70.0%, ages 50-74)⁴, CR (69.2%, ages 50-75)², and cervical (77.8%, women 21-65)³.

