- 5.2.1. Aim 4 is to conduct surveys with approximately N=250-280 eligible AI men and women.
 - 5.2.1.1. *Survey on Cancer of the Cervix (Women aged 21-49)*: N=50-60 AI women
 - 5.2.1.2. *Survey on Cancers of the Colon-Rectum, Breast, and Cervix (Women aged 50-75)*: N=100-110 AI women
 - 5.2.1.3. *Survey on Cancers of the Colon-Rectum and Prostate (Men aged 50-75)*: N=100-110 AI men

5.3. Aim 7

- 5.3.1. Aim 7 is to develop the interventions, including the small media, with about 12-15 TAP members (section 4.5) and 150 eligible AI men and women (we will invite 12-15 participants

in up to 15 total focus groups, with expectation that on average we will have 8-10 participants will attend) (section 4.8)

5.4. Aim 8

5.4.1. Aim 8 is to test the three interventions with about up to 150 eligible participants

Total between the Aims: N=706-850 participants

6. Study Timelines

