Because of participant and TAP member request following the focus groups, we will be mailing out the 3 brochures (breast, cervical, and colorectal) to all postal mailboxes in the Pueblo of Zuni prior to the intervention. There is one post office in the Pueblo that serves the households of Zuni, where all mail for residents are delivered. The study team will work with a local printer that will print and mail these brochures to each occupied (active) mailbox at the Zuni post office, approximately 1,530 mailboxes. We will not request any identifiable information from the tribe to complete this mailing rather we will use a method of mass mailing that will direct the mailout to “postal customers”, where the postmaster will deliver these brochures to active mailboxes in the Zuni Pueblo and appropriate zip code.

Aim 8: Pilot test (including qualitative methods) the multilevel/ multicomponent culturally and linguistically appropriate intervention strategies on outcomes such as: impact on screening practices; feasibility of implementation and acceptability of the intervention; and cost effectiveness of the intervention.

We will pilot test the intervention (INT) to document its: impact on screening practices; feasibility/acceptability; promoters/barriers to screening; effect positive changes on the MHOF constructs; and cost effectiveness. We will use quantitative followed by qualitative (focus group) mixed methods. We will recruit participants based on gender and age for cancer-specific screenings. In all, we will have up to 60 men age 45-75 (for CR cancer INT) 60 women age 45-75 (for breast [50-75 only], CR, and cervical cancer INTs) and 30 women age 21-44 (for cervical cancer INT). We will offer each group the specific cancer INT(s).

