13.1. The patient questionnaires will be analyzed utilizing approaches consistent with each data source. The structured questions will be exported from REDCap to a statistical software package for analysis. The qualitative responses to the questionnaire will be digitally recorded and transcribed for standard content analysis. The UNMCCC's Behavioral Measurement and Population Science Shared Resource will support the qualitative and quantitative data analysis efforts.

13.2. Quantitative Data Analysis (Aims 4 and 8): We will use descriptive statistics to characterize participant characteristics and their knowledge, attitude, screening practices, and preferred intervention strategy. We will use univariable and multivariable logistic regression analyses, with inclusion of modeling variables informed by the MHOF, to assess the relationship between socio-demographic variables, knowledge, and attitudes and beliefs on screening behaviors (Aim 4).

For Aim 8, for the primary outcome (completion of cancer screening), we will compare the number of cancer screening approaches (i.e., screenings for breast, CR, and/or cervical cancers) undertaken by study participants (based on age and gender), offset by the number of possible screening tests, using Poisson regression approaches between those who are and are not receiving active intervention. This will enable the estimation and comparison of screening uptake between treatment arms, even when there are different numbers of possible screening tests for groups of participants. We will account for within-cluster correlations using generalized estimating equations, and we will explore the impact on screening uptake of patient characteristics (e.g. sex) using fixed effects.

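### Aim 8's pooled screening count gives no estimate for any of the three interventions, and its exploratory sex effect is confounded with cancer type

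*Combined protocol and SAP*

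**What the plan says.** Section 13.2 names completion of screening as the primary Aim 8 outcome and states that "we will compare the number of cancer screening approaches (i.e., screenings for breast, CR, and/or cervical cancers) undertaken by study participants". A parenthesis then mentions age and gender without saying how they enter the model. The count is "offset by the number of possible screening tests, using Poisson regression approaches between those who are and are not receiving active intervention". The reason given for the offset is that arms can then be compared "even when there are different numbers of possible screening tests for groups of participants". Within-cluster correlation is to be handled by generalized estimating equations (GEE), and "we will explore the impact on screening uptake of patient characteristics (e.g. sex) using fixed effects". No cancer-type term, arm-by-cancer term or separate model by cancer is stated.

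Section 5.4.1 describes the purpose in the plural: "Aim 8 is to test the three interventions with about up to 150 eligible participants". Section 12 (Aim 8) gives the composition: "In all, we will have up to 60 men age 45-75 (for CR cancer INT) 60 women age 45-75". Those women are for CR and cervical, with breast only from age 50, and a further 30 women aged 21-44 are for cervical alone. Section 23.3 agrees: one cancer for men and for the younger women, two or three for women 45-75.

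**The concern.** Cancer type is nested in sex and age. The offset corrects for how many tests a person could have, not for which tests they are or how readily each is completed. Two things follow.

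- Eligibility (Section 4.9), flipcharts and sessions are specific to each cancer, but the model returns a single ratio. A gain in one cancer is diluted by the others, and the result cannot show which intervention worked.
- A sex term in this model sets a CR rate in men against a blend of breast, CR and cervical rates in women. A sex difference could be reported when men and women behave identically on the only test they share.

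**Working it through.** **Sample size.** 60 men + 60 women 45-75 + 30 women 21-44 = 150, which matches Section 5.4.1. No power statement for Aim 8 is given, so there is none to reproduce.

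**Possible tests at full enrolment** (maximum: every older woman is 50 or over and overdue for all three)

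| Group | CR | Cervical | Breast | Total |
|---|---|---|---|---|
| Men 45-75 (60) | 60 | 0 | 0 | 60 |
| Women 45-75 (60) | 60 | 60 | 60 | 180 |
| Women 21-44 (30) | 0 | 30 | 0 | 30 |
| All | 120 | 90 | 60 | 270 |

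All 60 of the men's tests are CR. Of the women's 210, 60 are CR (29%) and 150 (71%) have no male counterpart.

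**Sex ratio when sex has no effect within any cancer.** Let p be the uptake for each cancer, the same in both sexes.

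Ratio = {[60(p_breast + p_CR + p_cerv) + 30 p_cerv] / 210} / p_CR

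With the American Indian rates in Section 2 (breast 0.585, CR 0.419, cervical 0.639):

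- Women: 60 × 1.643 = 98.58; 30 × 0.639 = 19.17; sum 117.75; 117.75/210 = 0.561.
- Men: 0.419.
- Ratio: 0.561/0.419 = 1.34.

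| Uptake (breast, CR, cervical) | Source | Women | Men | Ratio |
|---|---|---|---|---|
| 0.585, 0.419, 0.639 | Section 2, American Indian | 0.561 | 0.419 | 1.34 |
| 0.700, 0.692, 0.778 | Section 2, White | 0.731 | 0.692 | 1.06 |
| 0.40, 0.40, 0.40 | assumed | 0.400 | 0.400 | 1.00 |
| 0.25, 0.40, 0.30 | assumed | 0.314 | 0.400 | 0.79 |
| 0.35, 0.20, 0.35 | assumed | 0.307 | 0.200 | 1.54 |

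The mix of tests matters less than the uptake rates. With the American Indian rates:

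- No breast tests at all (older women all 45-49): [60 × (0.419 + 0.639) + 19.17]/150 = 82.65/150 = 0.551, ratio 1.32.
- Older women overdue for CR only, an extreme case: (60 × 0.419 + 30 × 0.639)/90 = 0.492, ratio 1.18.
- Ages 45-75 only, women eligible for all three: 1.643/3 = 0.548, ratio 1.31. Adjusting for age therefore does not remove the problem.

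A simulation of the planned type of model (Poisson, log offset, arm and sex terms, robust errors, 1,500 runs, 75 per arm assumed, no sex effect within any cancer) gave a mean sex ratio of 1.35 with the American Indian rates. The sex term had p < 0.05 in 43% of runs. With the White rates that share was 6.5%, and with equal uptake 3.9%.

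**What pooling does to a cancer-specific effect.** Take the American Indian rates as control uptake and the weights 60, 120 and 90. Expected completed tests are 60 × 0.585 + 120 × 0.419 + 90 × 0.639 = 142.89 per 270.

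- +20 points in CR only: own ratio 0.619/0.419 = 1.48; pooled (142.89 + 24)/142.89 = 1.17.
- +20 points in breast only: own ratio 0.785/0.585 = 1.34; pooled (142.89 + 12)/142.89 = 1.08.
- +20 points in cervical only: own ratio 0.839/0.639 = 1.31; pooled (142.89 + 18)/142.89 = 1.13.
- +20 points in CR with −26.7 points in cervical: +24 − 24 = 0; pooled 1.00.

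**Precision by cancer.** Assuming 1:1 arms, the maximum per arm is 60 (CR), 45 (cervical) and 30 (breast). The 95% half-width for a difference at 50% uptake is 1.96 × √(2 × 0.25/n) = 18, 21 and 25 points. Power for 40% against 60% at two-sided 5% is 59%, 48% and 34%; 80% power would need 97 per arm.

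**The case against.** The strongest case for the plan is that this is a pilot of up to 150 people, and that a pooled count with an offset is a reasonable way to use all of them. Parts of Section 12 also describe one overall multicomponent intervention, for which one overall answer fits. The primary comparison is between arms. If the arms have a similar age and sex mix, both average over the same blend of tests, and the pooled ratio is a coherent measure of overall uptake. This stands. A reader might infer that pooling biases the arm comparison, but nothing in the documents shows that.

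The sex analysis is exploratory, and sex is only an example. The Section 2 rates are population screening rates, whereas Aim 8 enrols people never screened or overdue (Section 4.9), for whom no uptake figure is given. This also stands. It limits what can be said about size and direction, but not about the confounding itself.

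It can also be argued that the mention of age and gender in 13.2 implies analysis by group, and that the planned descriptive statistics may show uptake by cancer. The text says neither. Even a full split by age and sex group leaves up to 180 of 270 possible tests in women 45-75, where the cancers are still blended.

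**Conclusion.** The point holds as a gap in the planned analysis. As written, 13.2 yields one overall uptake ratio, no estimate for any of the three interventions, and an exploratory sex effect that cannot be separated from cancer type. That follows from the composition alone. The size of the sex artefact depends on uptake by cancer in overdue people, which is unknown: 1.34 with the American Indian rates, 1.06 with the White rates, 0.79 to 1.54 across the assumed sets, and 1.00 with equal uptake.

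Two stronger readings go too far. One is that women would necessarily appear to screen more than men: the artefact can run either way or vanish. The other is that the trial cannot answer for each cancer: the surveys in Section 12 are cancer-specific, so the limit lies in the planned model and not in the data. The pooled result may remain primary if it is labelled overall uptake.

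**What to change.** Change 13.2 as follows.

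- Use one yes/no record per participant per possible cancer screening, clustered on participant in the GEE, with a cancer-type term. Say that the participant is the cluster and that possible tests are counted by cancer, since neither is defined now.
- Keep the pooled arm comparison, labelled overall uptake. Beside it, report arm-by-cancer estimates with 95% confidence intervals, described as estimates and not powered tests. A cancer-type main effect alone is not enough, because it still gives one common intervention effect. Maximum denominators over both arms are CR 120, cervical 90 and breast 60.
- Estimate any sex effect only on CR screening at ages 45-75, with up to 60 men and 60 women.

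This takes a few sentences and uses data already to be collected. The cost is wider intervals: roughly ±18 to ±25 points for differences by cancer if the arms are equal in size, and at most 120 people instead of 150 for the sex comparison. The arm-by-cancer estimates also need a defined comparison group. 13.2 refers to treatment arms, but the documents do not set out a comparison arm or an allocation for Aim 8, so that has to be stated as well.

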Implementation of quantitative (survey) data collection to document INTs' impact on screening. We will contact (in-person or phone call) interested participants and provide them with a study description (StudyDescription_Intervention_2022_10_26_V1). If participants are interested, the study will continue with eligibility (Eligibility_Screener_Intervention_2023_02_02_V2). If participants are eligible, they will provide contact information (ContactSheet_Intervention_2022_10_26_V1) for the purposes of scheduling the study activities. The study will provide a packet that will contain the consent letter (ConsentLetter_InterventionTesting_2023_02_02_V4) that describes the study, PI contact information, description of the overall benefits and risks of participation, and dates for the study activities (i.e., baseline [BL] survey, INT session, post-intervention survey). The contact sheet will also ask participants if they wish to be contacted for future studies. If participants wish to be contacted, this will form our convenience sample for recruitment for the qualitative data collection for Aim 8 (focus groups). We will be using a consent letter format to continue to minimize COVID-19 exposure and risks for both community members and study team. The study is also minimal risk (surveys and educational session on specific age-gender cancer through the use of cancer specific flipcharts and small media) and encourages standard of care. The packet will also contain a scheduling card to inform participants about the date and time for the next project activity (baseline survey, INT session, post-intervention survey, focus group). Zuni students and staff will administer the surveys. We will conduct 2 waves of outcomes evaluation surveys: BL and at follow-up (6-8 months post-INT). [NOTE: We will submit the surveys to the HRRC and SWTIRB for review and approval prior to conduct of the surveys.]

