Implementation of qualitative data collection to documents promoters/barriers to screening. After the follow-up surveys, we will conduct up to 6 focus groups with those that indicated interest on the post-intervention survey. The focus groups will include participants based on gender and age for cancer-specific screenings. The results of the post-intervention survey question on focus group interest had yielded a low number of potential focus group participants, therefore we will be combining those reporting they are “adherent” (up to date on their screening) or were “not adherent” (not up to date on screening) for each age and gender specific group. Assuming some degree of attrition, we will recruit up to 10-12 participants per focus group. The purpose is to explore factors conducive to complete a screening (i.e., navigation, harm/ benefit assessment, norms and support, acceptability of the test, and self-efficacy). Among participants who did not complete any exam, we will inquire about barriers (i.e., social norms and support, acceptability, home-testing) and their potential solutions (see “FocusGroupGuide_education program_V1_2023_09_27”). Data collection and analysis procedures are similar to those described for small media development (Aim 7). Before the session, we will obtain consent (see “ConsentLetter-InterventionFG_2023_09_27_V3”) and inform participants that we will digitally audio-record the session. We will provide a form following the FG to ask whether the participants received screening (FG screening question_V1_2023_09_27). Participants will not need to provide any other information other than this.

Based on a round of implementing focus groups, we will implement one-on-one interviews with participants as needed per gender and age for cancer specific screenings. Assuming some degree of attrition, we will recruit 5-7 individuals per cancer specific screening for interviews. The interviews will follow a semi-structured format with similar questions as the focus groups (InterviewGuide_education program_V1_2023_10_30). Before each interview, we will obtain consent (ConsentLetter-InterventionInterview_2023_10_30_V1) and inform participants we will digitally audio record the session.

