- 23.1. Each focus group participant will receive a merchandise card in appreciation of her/his time. For Aim 3, women aged 21-49 participating in focus group on cervical cancer will receive a \$50 merchandise card; and men and women aged 50-75 participating in focus groups inquiring about multiple cancers will receive a \$75 merchandise card. Each healthcare provider and TAP

members participating in the focus group will receive a \$50 merchandise card in appreciation of her/his time. Each focus group with the physicians and TAP members is expected to take 45 to 60 minutes, therefore the amount of money is a reasonable amount of compensation. For Aims 7, the focus group participants will meet for about 45-60 minutes and will receive a \$50 merchandise card in appreciation of their time. For Aim 8, the focus group and interview participants will meet for up to 2 hours and will receive a \$50 merchandise card in appreciation of their time.

- 23.2. Each participant who completes the survey (Aims 8) will receive a \$25 merchandise card in appreciation of their time. Each survey will take an average about 20 minutes to complete, therefore the amount of money is a reasonable amount of compensation. For Aim 4, surveys among men 50-75 years and women 21-49 years will average about 20 minutes and they will receive a \$25 merchandise card; whereas, the survey with women 50-75 years will average about 40 minutes and they will receive a \$50 merchandise card ... amounts that are reasonable for the time provided to participate in the study.
- 23.3. Each participant who completes the intervention session will receive a merchandise card at the end of the educational session. Men 45-75 years and women 21-44 years will receive \$25 merchandise cards since they are eligible for one educational session on one cancer. The educational session will be administered over 1 session, about 1-hour long. Women 45-75 years will receive \$50 merchandise cards because they may be eligible for screening on 2-3 different cancers (breast, cervical, colorectal). These educational sessions will be administered over 1-2 sessions, about 1-hour each.
- 23.4. Each member of the advisory panel will receive a \$100 merchandise card per meeting attended, up to 4 meetings over the life of the study. Each meeting is expected to take no more than 2 hours, therefore the amount of money is a reasonable amount of compensation for their level of expertise and experience.

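### The Aim 8 primary analysis compares people receiving and not receiving the intervention, but the study as described offers it to everyone and has no comparator

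*Combined protocol and SAP*

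**What the plan says.** Section 13.2 names completion of cancer screening as the Aim 8 primary outcome. It models the number of screenings completed, offset by the number possible for each person, "using Poisson regression approaches between those who are and are not receiving active intervention". It adds: "This will enable the estimation and comparison of screening uptake between treatment arms". Generalized estimating equations (GEE) handle within-cluster correlation, but the cluster is not defined and no time term is mentioned.

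Section 12 (Aim 8) recruits up to 60 men aged 45-75, 60 women aged 45-75 and 30 women aged 21-44, each labelled with the intervention(s) for that group, and states: "We will offer each group the specific cancer INT(s". The enrolment packet carries one schedule: "dates for the study activities (i.e., baseline [BL] survey, INT session, post-intervention survey". The session follows the baseline survey. On measurement: "We will conduct 2 waves of outcomes evaluation surveys: BL and at follow-up (6-8 months post-INT". Before any of this, brochures on the three cancers are mailed "to all postal mailboxes in the Pueblo of Zuni prior to the intervention".

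Section 23.3 sets a payment for completing the session in all three groups. Men and younger women get the smaller amount "since they are eligible for one educational session on one cancer". Section 5.4 gives a total of up to 150. Section 4.9 enrols people who have never had, or are overdue for, at least one listed test.

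**The concern.** The primary analysis needs two groups, one receiving the intervention and one not. The procedures describe only the first. No control, delayed-start, randomised or external group appears in the sections on eligibility, numbers, timelines, procedures, recruitment or compensation. Random selection is mentioned only for the streets where flyers are distributed; Aim 8 itself is a convenience sample (Section 20).

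An analyst following Section 13.2 would get no estimate, or would have to improvise a comparison. The improvised choices are attenders against non-attenders, or follow-up against baseline. Either can show an apparent benefit when there is none. A reader of the Aim 8 report could then credit the intervention with self-selection, or with screening that would have happened anyway. Impact on screening is the first outcome Aim 8 lists, so this concerns its main quantitative result.

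**Working it through.** **1. The plan's own figure.** Section 12 gives 60 + 60 + 30 = 150, which reproduces the total in Section 5.4. All 150 places belong to groups labelled with an intervention. The sum alone would not exclude a split within groups. The evidence against a split is the offer to each group, the single activity sequence and the timing of the session directly after baseline. There is no Aim 8 power calculation to reproduce.

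**2. Can the stated contrast be estimated?** In a regression with an intercept and an indicator for receiving the intervention, the indicator is 1 for everyone if all attend. The two columns are then identical, the design matrix has rank 1 instead of 2, and the rate ratio is not estimable.

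**3. If some do not attend.** Assume zero true effect and 40% uptake among attenders. The rate ratio is attender uptake divided by non-attender uptake:

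| Assumed non-attender uptake | Rate ratio |
|---|---|
| 20% | 0.40/0.20 = 2.0 |
| 30% | 0.40/0.30 = 1.33 |
| 40% | 0.40/0.40 = 1.0 |

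The ratio would fall below 1 if non-attenders screened more. Non-attenders may also have received the mailed brochures, so the contrast would be session against brochure alone.

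**4. If a before-after comparison was meant.** Among people overdue on a given test, baseline completion of that test is 0 by definition, so any change is upward. With k one-way changes the exact two-sided McNemar p-value is 2 × 0.5^k:
- k = 5: 0.0625
- k = 6: 0.031

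Six completions are 20% of 30, 10% of 60 or 5% of 120. Under zero true effect, the binomial chance of six or more among 60 overdue people is:

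| Assumed background uptake by follow-up | P(at least 6 of 60) |
|---|---|
| 5% | 0.079 |
| 10% | 0.563 |
| 20% | 0.988 |

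McNemar's test is not in the plan. It is used here only to show how little background screening would look like an effect.

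**5. What a single-arm analysis could deliver.** This does not measure the defect; it shows that the replacement is usable. Possible screenings, with women 45-75 overdue on one, two or three tests each:
- 60 + 60×1 + 30 = 150
- 60 + 60×2 + 30 = 210
- 60 + 60×3 + 30 = 270

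Assume uptake p = 0.40, no loss to follow-up and within-person correlation ρ. With n_i tests for person i and N tests in all, the variance of the total count is V = Σ n_i p(1−p)[1 + (n_i − 1)ρ], the log-scale standard error is √V/(Np), and the 95% interval is p × exp(±1.96 SE):

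| N | ρ | V | SE | 95% interval |
|---|---|---|---|---|
| 270 | 0 | 64.8 | 0.0745 | 34.6-46.3% |
| 270 | 0.6 | 116.64 | 0.100 | 32.9-48.7% |
| 150 | any (one test each) | 36.0 | 0.100 | 32.9-48.7% |

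For one binary outcome at 24/60, the Wilson interval is 28.6-52.6%.

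**The case against.** The best case for the plan is that this is a pilot with two survey waves, GEE suits repeated measures, and a before-after comparison may have been intended. Section 2 leaves efficacy testing to future studies. This lowers the stakes but does not resolve the conflict, because Section 13.2 speaks of arms and of people not receiving the intervention, and gives no time term.

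Several narrower objections carry weight:
- Payment in Section 23.3 depends on completing the session, and the endpoint in Section 7, follow-up surveys from all eligible participants, would suit a control arm too. Both are weak evidence. The conclusion rests on Section 12.
- The criteria in Section 4.9 are joined by OR. Someone with a recent colonoscopy but no recent stool test is eligible, so some participants may be up to date for a cancer at baseline and could lapse. One downward change against six upward gives an exact McNemar p of 2 × (1 + 7)/128 = 0.125, not 0.031. The illustration therefore applies only to people overdue on the test in question.
- The mailing does not by itself bias a session-versus-brochure contrast; it changes what is being compared.
- Clustering by session or household is conceivable, and loss would widen the intervals: 120 tests (an assumed 20% loss from 150) gives 32.1-49.8% by the same formula.

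None of these supplies a comparator.

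**Conclusion.** The concern holds. The Aim 8 primary analysis cannot be carried out as written on the design described: the contrast is either inestimable or a self-selected comparison. That follows from the text alone, needs no assumption about rates, and must be fixed before Aim 8 is analysed or reported.

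The size of any resulting error cannot be derived from the documents, which give no uptake, attendance, background screening or loss figures. Under the assumptions above, a null intervention could show a rate ratio anywhere from 1.0 to 2.0, or a nominally significant before-after rise with probability from 8% to 99%. Feasibility and acceptability do not depend on this contrast. The documents give no cost-effectiveness method, so that result is affected only if it uses a comparative effect.

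**What to change.** First state in Section 13.2 and in Section 12 (Aim 8) whether a comparator exists.

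- **If it does:** describe how it is formed, its size and its follow-up, and acknowledge that the brochure mailing also reaches local residents.
- **If it does not:** remove the wording about people not receiving the intervention and about arms. Make the primary analysis the proportion of screenings completed by follow-up among participants overdue for that cancer's screening at baseline. Report it per cancer and age/sex group with 95% confidence intervals, plus an overall estimate from the existing Poisson/GEE model and offset. Define overdue for each cancer from the baseline survey, given the OR criteria in Section 4.9, and name the participant as the cluster. Describe the result as uptake after the intervention, not as its effect.

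In either case, reconcile the follow-up time (12 months in Sections 6.4.1 and 7, 6-8 months in Section 12), since uptake depends on that window. No cost-effectiveness result should imply a comparative effect without a comparator.

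The cost is a wording change with no new data collection. Section 12 reports that "The results of the post-intervention survey question on focus group interest had yielded a low number of potential focus group participants", so follow-up responses already existed; the amendment should be dated and labelled as made after follow-up data collection had begun. What is given up is a causal claim that the described design cannot support. If a comparator was intended but never recruited, a concurrent one may no longer be possible.
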